C2.4 Neurological and neuropsychological testing MCI testing Premorbid intelligence will be estimated with the Wechsler Test of Adult Reading²⁸. Dementia and MCI presence, in addition to activities of daily living (ADL) assessment using the Functional Activities Questionnaire²⁵, will be verified with the CDR²⁶ and the Montreal Cognitive Assessment (MoCA)²⁹. The MoCA is a brief test, and has a high sensitivity (90%) and specificity (87%) for detecting individuals with MCI and distinguishing them from individuals with normal cognition. In 114 participants with MCI that progressed to dementia and 51 that did not, 90.5% of participants with MCI with a MoCA score less than 20/30 at baseline converted to AD within the average follow-up period of 18 months, compared with 52.7% of participants with MCI above the cutoffs on both scores³⁰.

Patients who have been diagnosed as MCI, and who score <27 on the MoCA and have a CDR sum of boxes score of 0.5 – 4.0 along with verified neuropsychological performance on memory testing (e.g., Hopkins Verbal Learning Test – Revised [HVLT-R]) at or below 1.5 SD below the expected normative level will continue in the study³³. In some cases, MoCA scores at 27 will be considered for inclusion based on clinical consensus if the deficit in performance is specific to memory and there is evidence of MCI determined through other available metrics including HVLT-R, CDR and clinical record review. To verify amnestic MCI, in addition to review of recent neuropsychological/neurological testing data, the CDR, and administration of the MoCA in the current study protocol, we will administer a form of the HVLT-R³⁴. The short-form of the Boston Naming Test will be used to assess verbal/visual function. We will use the WMS-III digit span to determine effort during testing.

Healthy aged participants must score >=26 on the MoCA, have a CDR sum of boxes score of 0, and not be below 1.5SD of normative levels on the HVLT-R.

C2.6 Recruitment We will meet our recruitment objectives for participants based on the availability of cases from UF clinical medicine programs. UF informatics showed that 1139 patients with MCI were seen over the past four years at UF. Both PIs have clinics that see patients that are within the target differential (older patients with reported memory problems) and our department and two other departments with which we are affiliated (Aging and

Clinical and Health Psychology) that also evaluate patients that will meet our inclusion criteria. We may use certain UF services including I2B2 and Healthstreet.

Additionally, we will request a copy of the State of Florida Voter Registration registry. We will narrow down this list by voters that meet our age range (60-89) and send them an IRB approved flyer. This flyer would provide a brief overview of the study; as well as, study contact information for interested individuals.

C3.1 Procedural sequence The sequence and flow of the assessments to be conducted are as follows. Recruited participants will be screened over the phone after giving verbal consent. Participants will be mailed or emailed a map with directions to our study spaces if they request it. Participants who pass the initial phone screen will then be formally consented with a written ICF and then screened for inclusion/exclusion factors via interview, screening questionnaires, and review of medical records. Individuals who live farther away and are interested in the study but not wanting to make the drive without knowing they qualify for the study will have the option of having the intake administered by study staff at their (the potential participants) home. Any information and forms completed during this intake will be locked in a small filing cabinet and driven back to the University of Florida by study staff. All remaining study visits will be conducted at the University of Florida as usual.

Included participants will then undergo the MCI classification portion of the study, which characterizes the sample, collects covariates for mixed model analysis, and verifies group inclusion. Participants will be randomized between the two arms of the crossover sessions (initial tVNS vs. Sham). Behavioral portions of the testing will then be carried out twice, with at least one week between sessions (to avoid carryover effects). MRI scan will occur at least 72 hours from behavioral sessions.

C4.1 Intervention: tVNS Transcutaneous stimulation of the auricular branch of the vagus nerve will be applied. The auricular branch of the vagus projects to the brain stem and is accessible via electrical stimulation through surface electrodes. Stimulation produces vagus sensory evoked potentials, whereas stimulation of nearby regions does not. tVNS will be performed during the cognitive battery. tVNS will also be performed during fMRI. We may use two different stimulator devices. For the tasks outside of the scanner, we may use the Digitimer SD7A or a stimulator from Biopac. The Biopac stimulator is also MRI safe and thus, in the scanner, we will use the stimulator designed for MRI use from Biopac. This stimulator model is already in use at AMRIS. Both devices are capable of the same specs in terms of stimulation parameters.

C4.2 Electrode placement and stimulation The same type of electrodes will be used for both the MRI and lab based stimulation sessions. These are MRI safe electrodes and will be placed over the auricular branch of the vagus, held in place with adhesive gel. For the control condition, electrodes will be placed on the earlobe using the same electrodes. The ground electrode for tVNS will be placed just anterior to the tragus to minimize off-target stimulation per local pilot protocol, and the sham ground will be on the opposite side of the earlobe. Previous research has demonstrated that with tVNS versus stimulation of the ear lobe, fMRI showed BOLD-signal changes in the hippocampus, parahippocampal gyrus and the middle and superior temporal gyrus, as well as in the insula, precentral gyrus and the thalamus. In contrast, ear lobe stimulation did not show similar changes on fMRI³⁵. Stimulus will be set at 5-10V pulses and will be delivered at 20Hz, 100 μ s pulse width consistent with our pilot stimulus protocol and within the range of published stimulus parameters^{13,35-43}. Stimulus intensity for sham and tVNS will be ramped from 0 to the threshold of discomfort, then reduced to 80% of threshold, a level which is tolerable, as per local pilot protocol and prior investigations^{13,37-39,42}. Intensity level is expected to be between 4mA-15mA based on our pilot

data and prior reports, though subjects who express no discomfort may go beyond these levels, and subjects who express discomfort early may go below.

C5.1 MRI protocol We will use a research dedicated scanner in the UF Advanced MRI and Spectroscopy (AMRIS) facility. The scanning sequences will take ~1-1.5 hours to acquire and may include: 1) Structural MRI, 2) Diffusion Tensor Imaging (DTI). 3) fMRI 4) Magnetic Resonance Spectroscopy

Subjects will be provided a de-identified DVD with their structural scans if they request it. We will also mail copies of the DVD to subjects if they request it.

Task fMRI We will present the fMRI task (2-Back) using E-Prime software (Psychology Software Tools, Inc., Pittsburgh, PA) viewed through a double-mirror attached to the head coil. An MRI-compatible response box attached to the stimulus presentation computer will collect performance data.

2-Back. Verbal working memory will be assessed on a 2-Back and 0-back task, as in past studies^{19,47}. In both conditions, consonants are visually presented. In the 0-back condition, participants determine if each stimulus is the same or different from the previous stimuli, responding by binary button press. In the 2-back condition, participants respond yes if a stimulus is the same as the consonant two letters earlier, both the 0 and 2-back contain 33% targets. 8 blocks of both the 0-back and 2-Back conditions are pseudo-randomized across two 6-minute runs. Accuracy and reaction times are recorded.

C5.5 tVNS cognitive testing We will test the impact of tVNS with the following cognitive tests using:

- Repeatable Battery for the Assessment of Neuropsychological Status story learning and recall,
- Wechsler Memory Scale-IV Paired Associates I & II
- Phonemic and semantic fluency tests
- Paced auditory serial addition test (PASAT)
- WAIS-IV Digit Span (working memory) and Digit-symbol Coding ⁴⁸
- Rey Auditory Verbal Learning Test (RAVLT)
- ARCPT
- Trails
- tVNS or sham will be active throughout testing.

Possible Discomforts and Risks:

Non serious adverse events:

Non serious adverse events are defined as conditions that may be unpleasant and bothersome to the participant that do not require discontinuing the study. Study staff will be directly observing or participating in the execution of the research protocol and will contact the principal investigator or hospital staff as necessary should any adverse event occur. Should participants experience an adverse event outside of the contact periods, such as after the culmination of the research, they will be able to contact the principal investigator through the contact sheet provided during the consenting process.

Neuropsychological and behavioral testing will be conducted during the course of this study. Participants may experience fatigue and feelings of frustration while completing the cognitive tests. They may also feel of inadequacy if they do not complete all items on tests or can not recall all items on memory test. As part of the enrollment process and during each testing session, participants are reminded that the tests in this research project were chosen to be challenging and the most people do not complete all items of each test.

Transcutaneous Vagal Nerve Stimulation (tVNS) is considered to be safe application of the well established transcutaneous electrical nerve stimulation technology. tVNS has few potential risks, skin irritation at the site of stimulation due to skin prep or to sustained exposure to the conductive gels used to maintain electrical conductivity and conduct.

Adverse events:

Adverse events are unlikely to occur during the proposed research protocol, however precautions are in place in case of an unexpected adverse event. An adverse event (AE) is defined as any unfavorable and unintended sign (including an abnormal laboratory finding), symptom, or disease temporally associated with the intervention irrespective of whether it is considered related to the intervention.

Serious adverse events (SAEs):

SAEs are defined as events that may be harmful to the participant and/or may be serious enough to warrant either temporary or permanent discontinuation of the study intervention, either because they are intolerable or because they are judged to be potentially harmful. All serious adverse events require immediate reporting and an assessment of the implications for the continuation of the study and/or modification of the consent form. SAEs include events which: are acute or life threatening; result in prolonged, permanent or severe disability; induce another severe illness including worsening of a pre-existing condition, injury or accidents; require an inpatient hospitalization or surgical procedure, or a treatment to prevent a serious event; result in death. During each visit, participants will log any health-related problems or symptoms they are experiencing during structured interviews. Should participants experience a serious adverse event outside of the contact periods, including after the culmination of the research, they will be asked to contact the principal investigator through the contact sheet provided during the consenting process. These reports will be reviewed by study staff before allowing the participant to continue if research has not completed. All adverse events will also be categorized according to the likelihood that they are related to the study intervention. Events will be labeled either definitely, probably, possibly or unrelated to the study intervention and will be reported to the IRB and UF research service in accordance with regulatory requirements. Minor adverse events will be reported at the time of annual review. Both the principal investigator and the study staff will review the study regularly to examine reports of adverse incidents and evaluate study participant recruitment and study follow-through. Throughout the course of the study, information regarding issues deemed critical to the study or to the safety of research participants will be provided to the principal investigator and other study staff as needed. As a result of receiving this critical information, a meeting to discuss this information may be convened including the mentoring team. Information deemed critical would include: serious and non-serious adverse events that may occur; suspicion of scientific fraud or misconduct; incidental findings; any other issues which may warrant protocol changes or modifications.

Documentation of training on protection of human participants:

will be maintained by the University of Florida IRB. All key personnel on the study have successfully completed and will maintain certification from the University of Florida for mandatory education in human research subjects' protection, protection of personally identifiable information, and HIPAA compliance. This includes Collaborative Institutional Training Initiative (CITI) and Institutional Review Board IRB training

Potential benefits to participants and others:

There is no direct benefit to the participants in the study beyond compensation for travel and participation and, if requested, a copy of their assessments. These neuropsychological results may prove to be clinically valuable, but are not available because of any specific anticipated clinical purpose. The major potential benefit to patients with MCI as a group is through advances in our understanding of specific behavioral and neurophysiological outcomes of tVNS, especially with regard to its impact on cognition. This may lead to therapeutic clinical trials in subsequent studies. Improved treatments for MCI will help patients by improving quality of life via extension of independence and social participation capabilities.

Conflict of interest statement:

There are no real or potential conflicts of interest with regard to this research project. The research was conducted in the absence of any commercial or financial relationships that could be explained as a potential conflict of interest.

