Hypothesis 2: Research has demonstrated that neurodegeneration of medial temporal structures is the best antecedent MRI marker of imminent conversion to AD, with decreased hippocampal volume (left > right) being the most robust. Since the hippocampus receives direct input from the NTS as well as norepinephrine from the LC, those participants with MRI evidence of degeneration of the hippocampus/entorhinal cortex (its direct path connections (using diffusion tensor imaging [DTI])) *will improve during tVNS and the degree of improvement may be related to the degree of atrophy.*

Hypothesis 3: Those patients with MCI who have baseline memory impairment including reduced working memory and poor retrieval with intact recognition will improve with tVNS.

Hypothesis 4: Since norepinephrine is important for the function of the prefrontal-executive systems, patients with deterioration of prefrontal cortex as evidenced by atrophy and/or white matter integrity loss will show improvements in retrieval and working memory with tVNS as assessed by cognitive testing (digit span, free retrieval memory after a delay) and *the degree of improvement may be related to the degree of structural abnormality.*

7. Research Plan: Experimental design The design of the study is a hybrid, crossover trial structure with randomized and counterbalanced order of tVNS or sham tVNS (to control for ability to detect stimulation/placebo effects) administration (see *table 1 for basic design elements*). This will allow us the benefits of both a parallel and crossover design in that we will have equal numbers of subjects who have received sham or tVNS at time point 1 allowing a between subject analysis, while also allowing a crossover analysis. This design also enables the assessment of potential carryover and practice effects. Participants will attend four contact periods: 1) consent, inclusion screening, MRI eligibility and screening, structured history interview; 2) MRI scan; 3) and 4) stimulus sessions separated by at least 7 days, each consisting of the experimental protocol described below.

Intervention	Predictor	Outcome
tVNS versus sham stimulation (counterbalanced)	Baseline/sham cognitive performance	Cognitive performance - Memory, executive function
	Hippocampal/entorhinal volume	
	White matter variables	

Table 1: Intervention, predictors, and outcomes

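### No symptom interview follows the second stimulus session, so later events are recorded only if the participant reports them

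*Protocol*

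**What the plan says.** Section 7 of the Protocol (Experimental design) fixes the schedule: "Participants will attend four contact periods". The first is consent and screening, and the rest are "2) MRI scan; 3) and 4) stimulus sessions separated by at least 7 days". Nothing is listed after the second stimulus session.

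The safety text is under Possible Discomforts and Risks. Active collection takes place at visits: "During each visit, participants will log any health-related problems or symptoms they are experiencing during structured interviews". Outside visits the participant must make the contact. For non-serious events, including any that arise after the study ends, "such as after the culmination of the research, they will be able to contact the principal investigator through the contact sheet" describes the route. For serious events, "they will be asked to contact the principal investigator through the contact sheet provided during the consenting process". An adverse event includes any "disease temporally associated with the intervention irrespective of whether it is considered related to the intervention", with no number of hours or days attached. Every event is then to be classified: "Events will be labeled either definitely, probably, possibly or unrelated to the study intervention".

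On allocation, section 7 states that "we will have equal numbers of subjects who have received sham or tVNS at time point 1". SAP C6.2 gives an enrolment of 60. The SAP contains no adverse event analysis.

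**The concern.** In a crossover whose last contact is itself an exposure, the two sessions get different safety follow-up. After session 1 the participant returns at least 7 days later and is interviewed. After session 2 no one asks.

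Staff observation and the visit log cover what happens during session 2. They do not cover a reaction that appears after the participant has gone home. The one tVNS risk that the Protocol names is skin irritation from skin preparation or prolonged gel contact, and that could plausibly show itself later, although the Protocol does not describe it as delayed.

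Self-report is a weaker source in this population. C2.4 selects MCI participants for memory scores at least 1.5 SD below the norm. The contact sheet is handed over at consent. In section 7's order, with the MRI at least 72 hours from the sessions (C3.1) and the sessions at least 7 days apart, consent precedes session 2 by at least 3 + 7 = 10 days.

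At stake is how much the trial can say about delayed effects of tVNS. SAP C6.2 intends the data to inform the feasibility of a larger trial.

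**Working it through.** The plan states no figure on this point, so the check is a trace of the schedule followed by a sizing of the gap.

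**Inputs**
- Total of 60 participants (SAP C6.2).
- Two sequences, tVNS-sham and sham-tVNS (SAP C6.1), in equal numbers (Protocol section 7), so 60 / 2 = 30 each.
- Symptom interviews at visits only (Protocol, serious adverse events).
- No contact after session 2 (Protocol section 7).

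**Check of the 30/30 split.** SAP C6.2 claims 90% power at d = 0.854 from first-period data. With 30 per group, the noncentrality is 0.854 / √(2/30) = 3.31 on 58 degrees of freedom. The two-sided 0.05 power is then 90.2%, so the SAP also assumed 30 per group.

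**Trace by sequence**

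| Sequence | n | Interview after stimulus-session tVNS | Interview after sham |
|---|---|---|---|
| tVNS-sham | 30 | Yes, at session 2, at least 7 days later | None |
| sham-tVNS | 30 | None | Yes, at session 2, at least 7 days later |

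Solicited contact therefore follows 30 of 60 stimulus-session tVNS exposures (50%) and 30 of 60 sham exposures (50%).

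**Does this bias a comparison of conditions?** The chance that an event is recorded depends on the period. Each condition falls in each period for 30 participants, so the two conditions are under-recorded to the same extent on average, given similar completion of both sequences. The loss is of information: for delayed events each participant has one solicited period and one unsolicited period, so solicited data support only a between-participant contrast.

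**What the extra 30 would add.** If no events are seen in n followed participants, the exact one-sided 95% upper limit on the event rate is 1 − 0.05^(1/n):
- n = 30: 1 − 0.05^(1/30) = 9.5%
- n = 60: 1 − 0.05^(1/60) = 4.9%

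The chance of seeing at least one event at true rate p is 1 − (1 − p)^n. The documents give no rate, so the values of p are assumptions:

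| Assumed p | n = 30 | n = 60 |
|---|---|---|
| 2% | 45.5% | 70.2% |
| 5% | 78.5% | 95.4% |
| 10% | 95.8% | 99.8% |

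Both calculations assume that the interview detects every delayed event. As worded, it asks about symptoms being experienced at the time, so a reaction that has already cleared could be missed.

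**The case against.** The strongest defence is that this is a short mechanistic study with cognitive outcomes and an intervention that the Protocol regards as low risk. Observation in session plus a passive route afterwards is a defensible choice, and nothing in the documents contradicts it. Staff are present at both sessions, and the symptom log applies at session 2. MCI participants must be independent in daily and instrumental activities (C2.2), those with dementia are excluded (C2.3), and healthy older adults are enrolled as well (C2.1). tVNS is also given during fMRI (C4.1), and in section 7's order both sessions follow the scan, so scanned participants in either sequence are interviewed after one tVNS exposure. The consent pages were removed from the available text, so any instructions there cannot be seen.

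Much of this stands. It makes the point a minor one, but it does not supply a solicited contact after the last exposure.

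A reader might infer three stronger things that the documents do not support:
- **That the tVNS-versus-sham adverse event comparison is biased.** The gap follows period, and condition is counterbalanced across periods. The SAP also plans no such comparison.
- **That session 1 has a full week of surveillance and session 2 none.** Session 1 is followed by one later interview, worded around current symptoms. Counting solicited person-days would overstate what it provides.
- **That a particular number of tVNS events will be missed.** No delayed-reaction rate is given, and participants can still volunteer events.

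**Conclusion.** The gap is real and small. About half of the stimulus-session tVNS exposures (30 of 60), and equally half of the sham exposures, have no solicited contact afterwards. The consequence is lost safety information after the final exposure.

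This rests on four assumptions:
- The sequences are equal in size.
- The 60 in SAP C6.2 are all the participants randomised. The SAP describes them as having MCI, and no number is given for the healthy group.
- The MRI is the second contact, as section 7 numbers it. C3.1 gives only the 72-hour separation; an MRI held last would itself be a later visit.
- For the 9.5% and 4.9% limits, the interview detects the events that occur.

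It is an inexpensive improvement, and it does not affect the cognitive analyses.

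**What to change.** Add one structured telephone symptom interview about 7 days after session 2, for every participant who attends that session. Word both this call and the session 2 visit interview to ask about any symptoms since the previous session, including those that have resolved. Without the wording change, the call would share the weakness of the existing interview.

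The cost is one short call per participant (60 calls if all complete) by existing staff, who already screen by telephone (C3.1), plus one sentence in the safety section of the Protocol. The SAP's planned analyses need no change.
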